### 2 DATA SOURCE

PATS: BMI, procedure codes, CPB time and aorta clamp time, procedure date, date and time for admission and discharge ICU.

ICCA: length of stay ICU (if missing in PATS)

Biochemical data: creatinine

The Danish National Patient Register: age, sex, date of death

Perfusionist charts: CPB time and aorta clamp time (if missing in PATS)

Sundhedsplatformen: type of surgery, previous PCI, AMI within 90 days of surgery, hypertension, diabetes mellitus, smoking status, left ventricle ejection fraction (LVEF), NYHA, CCS, date of discharge hospitalisation, length of stay ICU (if missing in PATS), and the following defined according to the EuroSCORE II; extracardiac arthropathy, mobility status, previous cardiac surgery, chronic lung disease, active endocarditis, critical preoperative state and pulmonary hypertension,

The blood samples for the study were drawn preoperatively or within the first 24 hours of surgery (only preoperative data for hsCRP included) and stored in the Persimune Biobank or two other biobanks at Dept. Cardiothoracic Anaesthesiology and Dept. Cardiothoracic Surgery, Rigshospitalet (registered [name], PhD and [name], respectively). The analysis is performed using commercially available analyses (suPARnostic® kit (validated to measure suPAR concentrations between 0.6 and 22 ng/mL) (ViroGates)). HsCRP will be measured by high sensitivity CRP assays (Tina-quant hsCRP latex assay (validated to measure CRP concentrations between 0.3 - 20 mg/L) (Roche/Hitachi)). In patients with CRP>20 mg/L a regular CRP-measurement will be performed.

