Patients (≥ 18 years) undergoing elective on-pump cardiac surgery at the department of Cardiothoracic Surgery at Rigshospitalet, Denmark (isolated coronary artery bypass graft (CABG), single and multiple valvular procedures, combined CABG and valvular surgery, and others) and have given informed consent, is included. Exclusion criteria is; Perioperatively cancelling the surgery due to anatomic challenging findings, sudden change to off-pump coronary artery bypass (OPCAB) surgery, death prior to surgery and project blood samples not available.

Approximately 1000 patients will be enrolled in the biobank between 2012 and 2018 and will be included in the study. Data collection and analysis of the biomarkers is expected to be performed in 2019. The statistical analysis, writing of the manuscript and submission to a peer-reviewed journal is expected to be conducted in primo 2020. The study is approved by The Regional Committee on Health Research Ethics and the Data Protection Agency.

GENERAL INFORMATION

Protocol title: Predictive value of suPAR and hsCRP on postoperative mortality in 951 patients undergoing elective on-pump cardiac surgery.

Investigators:

Primary responsible:

[name] [name]
Rigshospitalet, University Hospital Copenhagen
Dept. Cardiothoracic Anaesthesiology
Copenhagen, Denmark

Senior responsible:

[name] [name], PhD, DMSc, Professor
Rigshospitalet, University Hospital Copenhagen
Dept. Cardiothoracic Anaesthesiology
Copenhagen, Denmark

[name] [name], PhD, Dept. Cardiothoracic Anaesthesiology, Rigshospitalet
[name], PhD, DMSc, Associate professor, Dept. Clinical Immunology, Rigshospitalet
[name], Ass. professor, Section of Biostatistics, University of Copenhagen.
[name], PhD, consultant, professor, centre director, the centre for cardiac, vascular, pulmonary and infectious diseases, Rigshospitalet

Collaborators:

PERSIMUNE, Department of Infectious Diseases, Rigshospitalet, Copenhagen University Hospital

The Department of Clinical Biochemistry, Rigshospitalet, Copenhagen University Hospital

Section of Biostatistics, University of Copenhagen.

RATIONALE & BACKGROUND INFORMATION

Hypothesis

We hypothesize that biomarkers reflecting a pro-inflammatory disease state at baseline; the soluble urokinase plasminogen activator receptor (suPAR) and high sensitivity C-reactive protein (hsCRP), can be used as preoperative predictors of outcome after cardiac surgery.

Aim

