#### **CONTENTS**

#### **1 INTRODUCTION**

Outcome after cardiac surgery is currently built on risk stratification based on patient demographics, comorbidities, physiological reserve and procedural variables, but these parameters explain only a minor part of the observed variation in perioperative complications between patients. A recent trend in risk modelling has been the addition of various biomarkers to supplement clinical risk predictors. By identifying predictive parameters of postoperative outcome such as biomarkers, future prevention- and treatment strategies for high risk patients may be developed and could potentially reduce morbidity and mortality after cardiac surgery and possibly in the future introduce the great opportunity of personalized medicine. One of the most important contributors to morbidity after cardiac surgery is the systemic inflammatory response syndrome (SIRS). The inflammatory response is triggered by the combination of surgical trauma, activation of blood components in the extracorporeal circuit on cardiopulmonary bypass, ischemia/reperfusion injury and endotoxin release. This inflammation most likely plays a central role in the development of all vital organ failures postoperatively including acute kidney injury, perioperative myocardial infarction, respiratory failure and stroke (Laffey et al. 2002, Karkouti et al. 2009, Kertai et al. 2015).

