The fundamental role of inflammation in cardiovascular disease has prompted interest in the predictive capability of numerous biomarkers that detect subclinical levels of inflammation. Formation of atherosclerotic plaques is proven to be influenced by inflammation, and soluble urokinase plasminogen activating receptor (suPAR) and High-sensitivity C-Reactive Protein (hsCRP) highlight different elements of inflammatory biochemical pathways linked to cardiovascular risk (Desmedt et al. 2017). CRP is involved in the trigger process of vascular remodelling and is positively associated with anthropometric measures where suPAR is linked to endothelial dysfunction, subclinical organ damage and atherosclerotic disease burden. SuPAR and hsCRP have been studied in infectious disease as well as in cardiovascular disease but the relationship to cardiovascular surgery outcome has only recently been explored. CRP is an acute-phase protein produced by the liver in response to several cytokines released from leukocytes during inflammation in response to infection or trauma. High-sensitivity CRP (hsCRP) measures low levels of CRP with increased sensitivity. SuPAR is a novel biomarker that correlates significantly with cardiovascular events and outperforms traditional markers of inflammation in prognosticating a range of cardiovascular events. SuPAR is released into the circulation by cleavage of the membrane-bound uPAR from various cells, including inflammatory and endothelial cells (Hodges et al. 2015). HsCRP has received a lot of attention regarding screening, reclassification and prediction of treatment response in patients suffering from cardiovascular disease and elevated levels of hsCRP preoperatively was found to be associated with increased risk of postoperative cardiovascular events after on pump coronary artery bypass grafting surgery (Balciunas et al., 2009).

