## 4 ANALYSIS SETS/ POPULATIONS/SUBGROUPS

The population includes adult patients ( $\geq$ 18 years) undergoing cardiac surgery at department of Cardiothoracic Surgery at Rigshospitalet, Copenhagen University hospital, Denmark.

Inclusion Criteria:

• Patients planned for elective on-pump cardiac surgery (isolated coronary artery bypass graft (CABG), single and multiple valvular procedures, combined CABG and valvular surgery, and others) and have given informed consent on delivering a blood sample for the biobank.

Exclusion Criteria:

• Peroperatively cancelling the surgery due to anatomic challenging findings, sudden change to offpump coronary artery bypass (OPCAB) surgery, death prior to surgery and project blood samples not available.

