### **5 ENDPOINTS AND COVARIATES**

### Primary objective

1. Association of preoperative suPAR values in relation to the censored time-to-event outcome "death from any cause" [Time Frame: from index surgery to date of data collection]

Secondary objectives:

- 2. Association of preoperative hsCRP values in relation to the censored time-to-event outcome "death from any cause" [Time Frame: from index surgery to date of data collection]
- 3. Assess whether adding suPAR, hsCRP or combined suPAR+hsCRP measurements improves predictive accuracy of EuroSCORE II [Time Frame: from index surgery to 30 days postoperative]
- 4. Sensitivity of the models; EuroSCORE II, suPAR, hsCRP, suPAR+hsCRP, EuroSCOREII+suPAR, EuroSCOREII+hsCRP and EuroSCOREII+suPAR+hsCRP in relation to the time-to-event outcome "death from any cause" [Time Frame: from index surgery to 30 days postoperative]
- 5. Specificity of the models; EuroSCORE II, suPAR, hsCRP, suPAR+hsCRP, EuroSCOREII+suPAR, EuroSCOREII+hsCRP and EuroSCOREII+suPAR+hsCRP in relation to the time-to-event outcome "death from any cause" [Time Frame: from index surgery to 30 days postoperative]
- 6. Asses association between suPAR and hsCRP measurements

Other outcome measures:

- 1. 30 days mortality measured by a yes/no question of "all-cause mortality" [Time Frame: from index surgery to 30 days]
- 2. 1-year mortality measured by a yes/no question of "all-cause mortality" [Time Frame: from index surgery to 1 year]

Covariates to be used in the analysis in order of priority according to number of events:

1. Sex (female/male), age (continuous), current smoker (status preoperative: yes/no), diabetes mellitus (status preoperative: yes/no), creatinine (preoperative: continuous), CPB time (continuous) and aorta clamp time (continuous), AMI within 90 days (status preoperative: yes/no)

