### 7.1 STATISTICAL PROCEDURES

A table 1 with patient characteristics for the entire study population will be generated presenting frequencies (percent), mean  $\pm$  standard deviation (SD), and median (25–75% quartile), where appropriate. This table will include the following variables: age (continuous (years)), sex (male), body-mass-index/BMI (continuous (kg/m^2), diabetes mellitus (NIDDM/IDDM), arterial hypertension (yes), EuroSCORE II value (continuous (%)), smoking status (never/previous/active), precious PCI (yes), NYHA (I-IV), CCS class 4 (yes), left ventricle ejection fraction/LVEF (continuous (%)), Previous cardiac surgery (yes), chronic lung disease (yes), acute myocardial infarction (AMI) within 90 days of surgery (yes), pulmonary hypertension (no, moderate, severe), weight on the intervention (isolated CABG, single non CABG, 2 procedures, 3 procedures), surgery on thoracic aorta (yes), baseline creatinine (continuous ( $\mu$ mol/L)), hsCRP (continuous (mg/L)), suPAR (continuous (ng/mL)),

In addition, the following peri- and postoperative variables will be used for analysis: cardiopulmonary bypass/CPB time (continuous (min)), aorta clamp time (continuous (min)), length of stay – ICU (continuous (hours)), length of stay – Hospitalisation (continuous (days)).

A table 2 will be generated including relevant tests for association between the individual variables mentioned above and continuous values of suPAR and hsCRP, respectively.

We will fit Cox proportional hazards models to assess the association between preoperative suPAR and hsCRPvalues and death from any cause. The goodness-of-fit of the Cox model will be investigated and the model will be adapted as required to fulfil the model assumptions. The model will be adjusted for sex, age, current smoker, AMI within 90 days, diabetes mellitus, creatinine, CPB time and aorta clamp time. 30-days survival will be modelled using logistic regression. If we cannot find Cox and/or logistic models that fit the data, alternative models will be considered.

Receiver operating characteristics (ROC) curve and area under the curve (AUC) analysis will be performed comparing EuroSCORE II, suPAR, hsCRP, suPAR+hsCRP, EuroSCOREII+suPAR, EuroSCOREII+hsCRP and EuroSCOREII+suPAR+hsCRP. Sensitivity and specificity values will be included.

Regression analysis between suPAR and hsCRP measurement will be performed.

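### The primary exposure is called preoperative suPAR, but the sampling rule admits suPAR drawn up to 24 hours into or after surgery, with no timing term and no preoperative-only analysis

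*SAP*

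**What the plan says.** The protocol's hypothesis is that suPAR and hsCRP reflect a pro-inflammatory state at baseline and "can be used as preoperative predictors of outcome after cardiac surgery". The primary objective, the same in the protocol and in SAP section 5, reads "Association of preoperative suPAR values in relation to the censored time-to-event outcome" of death from any cause. SAP section 7.1 repeats the label for the model: "We will fit Cox proportional hazards models to assess the association between preoperative suPAR and hsCRPvalues and death from any cause".

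The sampling rule, in SAP section 2 and the protocol's Methodology section, is wider: "The blood samples for the study were drawn preoperatively or within the first 24 hours of surgery (only preoperative data for hsCRP included").

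The adjustment set in SAP section 7.1 is: "The model will be adjusted for sex, age, current smoker, AMI within 90 days, diabetes mellitus, creatinine, CPB time and aorta clamp time". The only sample-related exclusion in SAP section 4 is the absence of a project sample; the list ends "death prior to surgery and project blood samples not available". Timing of the draw is not a criterion.

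**The concern.** The rule contrasts draws within the first 24 hours of surgery with preoperative draws, so the second group must include samples taken during or after the operation. If every sample were preoperative, the hsCRP restriction would be redundant. Since it names hsCRP alone, late suPAR samples stay in.

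The SAP's own introduction gives reason not to treat the two kinds of sample as interchangeable. On surgery it says: "The inflammatory response is triggered by the combination of surgical trauma, activation of blood components in the extracorporeal circuit on cardiopulmonary bypass". On the marker it says: "SuPAR is released into the circulation by cleavage of the membrane-bound uPAR from various cells, including inflammatory and endothelial cells". It does not say how much suPAR changes over an operation.

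Four things are at stake.

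- **Label.** A value drawn after the start of surgery cannot support a claim of preoperative prediction, even if suPAR does not change. The same values would enter models of 30-day death offered as additions to a preoperative risk score.
- **Estimate.** A shift or extra noise in late samples attenuates the hazard ratio. If late-sampled patients also differ in baseline risk, the bias can go either way.
- **Comparability.** With hsCRP restricted and suPAR not, the two markers may be compared on different patients.
- **Survival to the draw.** Anyone sampled after surgery must have lived to the draw. This covers at most 24 hours, so it could matter mainly for 30-day mortality and hardly for the long-term Cox model.

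**Working it through.** **Text check.** The plan states no figure on this point, so there is nothing to reproduce.

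| Item | Where | Content |
|---|---|---|
| Exposure as named | Protocol hypothesis and objectives; SAP 3, 5, 7.1 | preoperative suPAR |
| Samples admitted | Protocol Methodology; SAP 2 | preoperative, or first 24 hours of surgery |
| Restriction to preoperative data | same | hsCRP only |
| Exclusions | Protocol Study design; SAP 4 | no timing criterion |
| Covariates | SAP 5, 7.1 | eight, none for sample timing |
| Missing data | SAP 6 | pairwise deletion; a late suPAR value is not treated as missing |
| Sensitivity analysis by timing | SAP 7.1 | none |

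Bypass time and clamp time are adjusted for, but they measure surgical exposure and do not show whether the blood was drawn before or after it. The protocol's only stability statement concerns frozen storage.

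**Illustration of size.** All inputs are assumed:

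- SD of log2 suPAR 0.6, so V = 0.36
- share of late samples f = 10–40%
- mean shift in late samples d = −0.6 to +0.6 log2 units
- added noise SD s = 0–0.4
- true hazard ratio 2.0 per doubling

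If lateness is unrelated to risk, the log hazard ratio shrinks by approximately

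λ = V / (V + f(1−f)d² + f·s²), and the observed HR = 2^λ.

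| f | \|d\| | s | Denominator | λ | Observed HR | Simulated Cox HR |
|---|---|---|---|---|---|---|
| any | 0 | 0 | 0.36 | 1 | 2.00 | 2.00 |
| 0.1 | 0.2 | 0.2 | 0.36 + 0.0036 + 0.0040 = 0.3676 | 0.979 | 1.97 | 1.98 |
| 0.3 | 0.4 | 0.4 | 0.36 + 0.0336 + 0.0480 = 0.4416 | 0.815 | 1.76 | 1.73 (up), 1.78 (down) |
| 0.4 | 0.6 | 0.4 | 0.36 + 0.0864 + 0.0640 = 0.5104 | 0.705 | 1.63 | 1.60 (up), 1.66 (down) |

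Up and down give the direction of the shift. The simulations, with about 12% deaths, check the approximation only; they add no information on the inputs.

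**If late-sampled patients differ in risk.** Suppose suPAR has no effect and the late group has 1.5 times the hazard, before covariate adjustment:

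log HR = f(1−f)·d·ln(1.5) / (V + f(1−f)d² + f·s²), with ln(1.5) = 0.405.

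- d = 0: HR 1.00.
- f = 0.1, d = 0.2, s = 0.2: 0.09 × 0.2 × 0.405 / 0.3676 = 0.020, HR 1.02.
- f = 0.3, d = 0.4, s = 0.4: 0.21 × 0.4 × 0.405 / 0.4416 = 0.077, HR 1.08.
- f = 0.4, d = +0.6, s = 0: 0.24 × 0.6 × 0.405 / 0.4464 = 0.131, HR 1.14. With d = −0.6, HR 0.88.

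**Quartiles.** By simulation, about 6% of all patients change quartile at f = 0.1, d = 0.2, s = 0.2. At f = 0.3, d = 0.4, s = 0.4 it is about 27% of all patients and 49% of those sampled late. With no shift and no noise it is 0%.

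**The case against.** The hsCRP-only rule may be deliberate. SAP section 1 calls CRP an acute-phase protein and links suPAR to endothelial dysfunction, subclinical organ damage and atherosclerotic burden. If suPAR hardly moves within 24 hours, pooling does no numerical harm, and nothing in the documents shows that it does move. This stands as a reason to call the size unknown. It does not justify the label, and the reviewed text neither states this reason nor tests it.

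Restriction is also not clearly better for testing the association. When lateness is unrelated to risk, pooling keeps roughly a fraction λ of the information and restriction keeps 1 − f. In the three attenuated cases tabulated, pooling keeps more: 0.979 against 0.90, 0.815 against 0.70, and 0.705 against 0.60. The order can reverse: at f = 0.1, d = 0.6, s = 0.4, λ = 0.36 / (0.36 + 0.0324 + 0.0160) = 0.88 against 0.90. The argument is fair, but it concerns power. It does not cover a late group with different risk, and it does not make the pooled exposure preoperative. It is a reason to accept the full cohort as primary only if the exposure is relabelled.

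Part of the protocol was not available for review; its contents list a section on anticipated problems. Absence is therefore established only for the text reviewed. The SAP sections on data source, analysis sets, covariates, missing data and statistical procedures, where a remedy would belong, were all available.

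**Conclusion.** The concern holds and should be fixed before analysis. The conflict between the named primary exposure and the samples admitted is certain from the text; the numerical harm is not. It depends on the share of late samples, on how suPAR behaves over surgery, and on whether late-sampled patients differ in risk, none of which the documents give. Under the assumed ranges the effect runs from nothing to a clear attenuation, and a null marker could show a modest spurious association in either direction. The reporting error does not depend on these assumptions: if the plan is followed as written, any late suPAR value will be presented as preoperative.

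**What to change.** Apply to suPAR the rule already set for hsCRP: the primary Cox model, the quartiles and all EuroSCORE II comparisons use only samples drawn before surgery. Report sample counts by timing (before surgery or later) and by biobank, and restate the analysed N. Use all samples in a sensitivity analysis stratified by or adjusted for sample timing, with follow-up starting at the draw where the draw time is known.

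If the full set is kept as primary, call the exposure perioperative suPAR, make no claim of preoperative prediction from it, and report the preoperative-only result alongside.

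The change needs SAP wording and a pre/post flag per sample, which the hsCRP restriction already requires. Exact draw times are not among the listed data fields and are needed only for the sensitivity analysis that starts follow-up at the draw. The price is a smaller primary set. With f = 10–40% assumed, 951 × (1 − f) leaves about 856 down to 571 patients. The standard error of the log hazard ratio grows by 1/√(1 − f), or 1.05 to 1.29, if the event rate is unchanged.

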#### **3 ANALYSIS OBJECTIVES**

This study aims to investigate whether preoperative levels of suPAR and hsCRP are associated with death after cardiac surgery. Further, to assess whether suPAR and hsCRP provides increased predictive accuracy of the clinical risk model EuroSCORE II. The purpose of the study is to gain knowledge on whether these inflammatory biomarkers might be able to reveal a pro-inflammatory disease state that represents a significant risk in patients undergoing cardiovascular surgery. Hence, these biomarkers may assist clinicians to gain more accurate risk identification and potentially compassionate treatment for high risk patients.

## 4 ANALYSIS SETS/ POPULATIONS/SUBGROUPS

The population includes adult patients ( $\geq$ 18 years) undergoing cardiac surgery at department of Cardiothoracic Surgery at Rigshospitalet, Copenhagen University hospital, Denmark.

Inclusion Criteria:

• Patients planned for elective on-pump cardiac surgery (isolated coronary artery bypass graft (CABG), single and multiple valvular procedures, combined CABG and valvular surgery, and others) and have given informed consent on delivering a blood sample for the biobank.

Exclusion Criteria:

• Peroperatively cancelling the surgery due to anatomic challenging findings, sudden change to offpump coronary artery bypass (OPCAB) surgery, death prior to surgery and project blood samples not available.

### **5 ENDPOINTS AND COVARIATES**

### Primary objective

1. Association of preoperative suPAR values in relation to the censored time-to-event outcome "death from any cause" [Time Frame: from index surgery to date of data collection]

Secondary objectives:

- 2. Association of preoperative hsCRP values in relation to the censored time-to-event outcome "death from any cause" [Time Frame: from index surgery to date of data collection]
- 3. Assess whether adding suPAR, hsCRP or combined suPAR+hsCRP measurements improves predictive accuracy of EuroSCORE II [Time Frame: from index surgery to 30 days postoperative]
- 4. Sensitivity of the models; EuroSCORE II, suPAR, hsCRP, suPAR+hsCRP, EuroSCOREII+suPAR, EuroSCOREII+hsCRP and EuroSCOREII+suPAR+hsCRP in relation to the time-to-event outcome "death from any cause" [Time Frame: from index surgery to 30 days postoperative]
- 5. Specificity of the models; EuroSCORE II, suPAR, hsCRP, suPAR+hsCRP, EuroSCOREII+suPAR, EuroSCOREII+hsCRP and EuroSCOREII+suPAR+hsCRP in relation to the time-to-event outcome "death from any cause" [Time Frame: from index surgery to 30 days postoperative]
- 6. Asses association between suPAR and hsCRP measurements

Other outcome measures:

- 1. 30 days mortality measured by a yes/no question of "all-cause mortality" [Time Frame: from index surgery to 30 days]
- 2. 1-year mortality measured by a yes/no question of "all-cause mortality" [Time Frame: from index surgery to 1 year]

Covariates to be used in the analysis in order of priority according to number of events:

1. Sex (female/male), age (continuous), current smoker (status preoperative: yes/no), diabetes mellitus (status preoperative: yes/no), creatinine (preoperative: continuous), CPB time (continuous) and aorta clamp time (continuous), AMI within 90 days (status preoperative: yes/no)

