PROTOCOL

Predictive value of suPAR and hsCRP on postoperative mortality in 951 patients undergoing elective on-pump cardiac surgery.

TABLE OF CONTENTS

| | |
|---|----|
| Project summary | 3 |
| General information | 4 |
| Rationale & background information | 5 |
| Study goals and objectives | 7 |
| Study design | 8 |
| Methodology | 9 |
| Safety considerations | 10 |
| Follow-up | 10 |
| Data management and Statistical Analysis | 10 |
| Quality Assurance | 11 |
| Expected Outcomes of the Study | 11 |
| Dissemination of Results and Publication Policy | 11 |
| Duration of the Project | 12 |
| Problems Anticipated | 12 |
| Project Management | 12 |
| Ethics | 13 |
| Informed Consent Forms | 14 |
| Financing and insurance | 18 |

PROJECT SUMMARY

Title: Predictive value of suPAR and hsCRP on postoperative mortality in 951 patients undergoing elective on-pump cardiac surgery.

The risk models currently used to predict outcome after cardiac surgery only explain a minor part of the observed variation in perioperative complications between patients. A recent trend in risk modelling has been the addition of various biomarkers to supplement clinical risk factors.

This study aims to investigate whether preoperative measurement of the inflammatory biomarkers soluble urokinase plasminogen activating receptor (suPAR) and High-sensitivity C-Reactive Protein (hsCRP) are associated with death after cardiac surgery. Further, to assess whether suPAR and hsCRP provides increased predictive accuracy of the clinical risk model EuroSCORE II. The purpose of the study is to gain knowledge on whether these inflammatory biomarkers might be able to reveal a pro-inflammatory disease state that represents a risk in patients undergoing cardiovascular surgery. Hence, these biomarkers may assist clinicians to gain more accurate risk identification and selecting compassionate treatment for high risk patients.

The study design is a retrospective observational cohort study conducted at The Department of Cardiothoracic Anaesthesiology, Rigshospitalet, in collaboration with University of Copenhagen and PERSIMUNE Centre of Excellence, Rigshospitalet.

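### One-year mortality is defined as a plain yes/no, although the last patients may lack a full year of follow-up; a Kaplan-Meier estimate at 365 days avoids the problem

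*SAP*

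**What the plan says.** SAP section 5 (Endpoints and covariates), under other outcome measures, gives "1-year mortality measured by a yes/no question", with a window from index surgery to 1 year. The protocol's list of other outcome measures has the same item.

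The dates are in the protocol's project summary: "Approximately 1000 patients will be enrolled in the biobank between 2012 and 2018" and "Data collection and analysis of the biomarkers is expected to be performed in 2019". Statistical analysis and writing follow, and "submission to a peer-reviewed journal is expected to be conducted in primo 2020".

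Enrolment can be read as the surgery date, because SAP section 2 states: "The blood samples for the study were drawn preoperatively or within the first 24 hours of surgery". The same section takes the date of death from a national register.

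The primary (suPAR) and first secondary (hsCRP) outcomes are handled differently: both are censored time-to-event outcomes running to the date of data collection. SAP 7.1 names Cox models for these, logistic regression for 30-day survival, and Kaplan-Meier plots by biomarker quartile. It names no method for the 1-year outcome. SAP section 6 handles missing values by pairwise deletion and does not say whether an incomplete first year counts as missing.

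**The concern.** A yes/no outcome at 1 year can be determined only for a patient who has died within the year or been observed for all of it. A patient operated on late in 2018 and alive at an extraction in, say, spring 2019 is neither. Whoever builds the dataset must then either count that patient as a survivor or leave the value missing. The first choice credits survival time that was not observed. The second removes patients because they were still alive, while keeping those from the same months who had already died. Both distort the proportion, in opposite directions, and the distortion falls on the most recently operated patients. At stake is the accuracy of a descriptive 1-year mortality figure, and of any tabulation of it by biomarker level. The plan's main inference is not at stake.

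**Working it through.** The documents give no share of patients with incomplete follow-up and no expected event count, so there is no plan figure to reproduce. The check is date arithmetic followed by a size estimate.

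**Inputs from the documents.** N = 951 (protocol title; the text says about 1000). Enrolment 2012–2018, with no months or yearly counts. Data collection in 2019, with no day given in the text reviewed.

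**Assumptions.** Even accrual from 1 January 2012 to 31 December 2018 (2557 days). True 1-year mortality 5%, with 2% and 10% as a range. None of these is in the documents.

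**Step 1: share without a full year.** Share = (365 − days from last surgery to data cut) / 2557.

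| Data cut | Calculation | Share | Patients of 951 |
|---|---|---|---|
| 1 Jan 2019 | (365 − 1)/2557 | 14.2% | 135 |
| 1 Apr 2019 | (365 − 91)/2557 | 10.7% | 102 |
| 1 Jul 2019 | (365 − 182)/2557 | 7.2% | 68 |
| 1 Oct 2019 | (365 − 274)/2557 | 3.6% | 34 |
| 31 Dec 2019 | (365 − 365)/2557 | 0% | 0 |

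**Step 2: other readings of the dates, 1 January 2019 cut.**
- Mid-2012 to mid-2018: 8.2% (and 0% from 1 July 2019).
- End-2012 to end-2018: 16.6%.
- Accrual ending at the start of 2018: 0%.
- Uneven accrual with 20% or 30% of patients operated on in 2018: 20% (190) or 30% (285).

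**Step 3: late patients counted as alive.** Take the late group as 951/7 = 135.9 at a 1 January cut. At 5% mortality their expected 1-year deaths are 135.9 × 0.05 = 6.8, out of 951 × 0.05 = 47.6 in all.
- Constant hazard: follow-up is spread evenly over 0–12 months, so about half these deaths fall after the cut. The exact figure is 3.4 missed; 3.4/47.6 = 7.1%, so 4.65% is reported instead of 5%.
- Early deaths more common: let a share p of 1-year deaths occur in the first 30 days. The fraction missed is [30 − 15p + 167.5(1 − p)]/365. For p = 1/3 this is 136.7/365 = 0.37, or 2.5 deaths (5.3%). For p = 1/2 it is 106.25/365 = 0.29, or 2.0 deaths (4.2%).
- 1 July cut, constant hazard: 0.8 deaths missed, under 2% relative.
- At 2% or 10% mortality with constant hazard, 1.4 or 6.7 deaths are missed at a 1 January cut; the relative error stays near 7%.

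**Step 4: late patients without a recorded death deleted.** Same case (5%, constant hazard, 1 January cut). Deaths observed: 47.6 − 3.4 = 44.2. Of the late group, 6.8 − 3.4 = 3.4 have a recorded death and stay; 135.9 − 3.4 = 132.5 are deleted. Reported mortality = 44.2/(951 − 132.5) = 44.2/818.5 = 5.4%.

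**Step 5: Kaplan-Meier at 365 days.** Late patients contribute the time observed and are then censored. With no one censored before day 365, the estimate is the simple proportion.

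**The case against.** The strongest reply is that the problem may never arise. The timetable puts the analysis in early 2020, deaths come from a register, and a vital-status pull at the end of 2019 would give every patient a full year. That stands, and it is why the range starts at 0%.

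A reader might infer that the plan codes late patients as survivors and so commits itself to a downward bias. The documents do not support this. Neither document says how an incomplete year is coded, and pairwise deletion could be taken to apply, which would push the figure upward. Deletion is no remedy: SAP section 6 describes missing data as arising from device or registration faults, whereas here the value would be missing because the patient was still alive at the cut.

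A reader might also take 14% as a maximum. It is one scenario, with even accrual and the earliest possible cut in 2019. Step 2 shows both lower and higher values.

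Nor can the plan be charged with having no data-cut date. The protocol's table of contents lists a section on the project's duration that is not in the text reviewed here, and a date could be there.

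Finally, the outcome is a minor one and no model is specified for it, so an effect on biomarker comparisons is hypothetical. That also stands. What remains is that a plain yes/no is valid only under some extraction dates, while an estimate valid under all of them is available from curves already planned.

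**Conclusion.** The point holds as a minor improvement. The yes/no definition of 1-year mortality is sound only if vital status is extracted at least a year after the last surgery. Under even accrual, the share of patients without a full year runs from 0% to about 14% depending on when in 2019 the data are cut, and more if 2018 was a heavy year. At an assumed 5% mortality and a 1 January cut, the reported figure could be about 4.65% if these patients count as alive, or about 5.4% if those without a recorded death are dropped. The direction is not fixed by the documents. The size rests on assumed accrual, mortality and timing of deaths.

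Only an outcome in the other category is involved. The primary suPAR analysis and the hsCRP time-to-event analysis are censored and are not affected.

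**What to change.** In SAP sections 5 and 7.1, replace the yes/no summary with 1-year mortality estimated as 1 minus the Kaplan-Meier survival at 365 days, with a 95% CI, overall and by suPAR and hsCRP quartile, censoring at the vital-status extraction date.

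The cost is about one sentence. The quartile curves are already planned, so only the overall curve and the reading at 365 days are added, and no new data are needed. The method assumes that late patients have the same first-year risk as earlier ones, which should be noted if risk changed over the enrolment years. If every patient turns out to have a full year of follow-up, the result is the simple proportion and nothing is lost.
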